6.4.4 Reporting of serious adverse events

All SAEs have to be reported, whether or not considered causally related to the investigational product, or to the study procedure(s). All SAEs will be recorded in the eCRF.

If any SAE occurs in the course of the study, then investigators or other site personnel inform appropriate AstraZeneca representatives within one day ie, immediately but **no later than the end of the next business day** of when he or she becomes aware of it.

The designated AstraZeneca representative works with the investigator to ensure that all the necessary information is provided to the AstraZeneca Patient Safety data entry site **within one calendar day** of initial receipt for fatal and life threatening events **and within five calendar days** of initial receipt for all other SAEs.

For fatal or life-threatening adverse events where important or relevant information is missing, active follow-up is undertaken immediately. investigators or other site personnel inform AstraZeneca representatives of any follow-up information on a previously reported SAE within one calendar day ie, immediately but **no later than the end of the next business day** of when he or she becomes aware of it.

Once the investigators or other site personnel indicate an AE is serious in the WBDC system, an automated email alert is sent to the designated AstraZeneca representative.

If the WBDC system is not available, then the investigator or other study site personnel reports an SAE to the appropriate AstraZeneca representative by telephone.

The AstraZeneca representative will advise the investigator/study site personnel how to proceed.

The reference document for definition of expectedness/listedness is the IB for olaparib.

6.4.5 Laboratory safety assessment

Blood samples for determination of clinical chemistry, haematology and coagulation will be taken at the times indicated in the Study Schedule (see [Table 2](#))

The following laboratory variables will be measured:

Full haematology assessments for safety (haemoglobin, red blood cells [RBC], platelets, mean corpuscular volume [MCV], mean corpuscular haemoglobin concentration [MCHC], mean corpuscular haemoglobin [MCH], white blood cells [WBC], differential white cell count and absolute neutrophil count should be performed at each visit and when clinically indicated. Coagulation [activated partial thromboplastin time {APTT} and international normalised ratio {INR}]) will be performed at baseline and if clinically indicated unless the patient is receiving warfarin.

Biochemistry assessments for safety (sodium, potassium, calcium, magnesium, glucose, creatinine, total bilirubin, gamma glutamyltransferase [GGT], alkaline phosphatase [ALP], aspartate transaminase [AST], alanine transaminase [ALT], urea or blood urea nitrogen [BUN], total protein, albumin, lactic dehydrogenase [LDH]) amylase and lipase will be performed.

Urinalysis by dipstick should be performed at baseline and then only if clinically indicated. Microscopic analysis should be performed by the hospital's local laboratory if required.

These tests will be performed by the hospital's local laboratory. Additional analyses may be performed if clinically indicated.

Any clinically significant abnormal laboratory values should be repeated as clinically indicated and recorded on the eCRF.

For blood volumes see Section [7.1](#)

6.4.6 Physical examination

For timing of individual measurements refer to study schedule (see [Table 2](#)).

A complete physical examinations will be performed including an assessment of the following:

Height (screening only), BP, pulse, and temperature at the screening visit and as outlined in the study schedule. Weight will be measured according to the study schedule.

Performance status will be assessed using the ECOG scale (reference [Appendix E](#)) at baseline and as outlined in the study schedule. The same observer should assess performance status each time.

6.4.7 ECG

6.4.7.1 Resting 12-lead ECG

ECGs are required within 7 days prior to starting study treatment, at 8 weeks after starting study treatment and at the follow up visit after patient has discontinued study medication and when clinically indicated.

Twelve-lead ECGs will be obtained after the patient has been rested in a supine position for at least 5 minutes in each case. All 12-lead ECGs should be recorded while the patient is in the supine position. The investigator or designated physician will review the paper copies of each of the timed 12-lead ECGs on each of the study days when they are collected.

ECGs will be recorded at 25 mm/sec. All ECGs should be assessed by the investigator as to whether they are clinically significantly abnormal / not clinically significantly abnormal. If there is a clinically significant abnormal finding, the investigator will record it as an AE on the eCRF. ECGs are required within 7 days prior to starting study treatment, at end of cycle 1, at the final follow up visit and when clinically indicated. A copy of the ECG indicating the study number, without patient identifiers will be collected by the study monitor.

6.4.8 Vital signs

6.4.8.1 Pulse and blood pressure

Supine BP and pulse rate will be measured using an appropriate cuff size, after patient has rested for at least 10 minutes. For the timing of assessments refer to the study plan (see [Table 2](#)).

The date and time of collection and measurement will be recorded on the appropriate eCRF.

6.4.8.2 Body temperature (Not Applicable)

6.4.9 Other Safety Assessments

6.4.9.1 Serum or urine pregnancy test

Two pregnancy tests on blood or urine samples will be performed for pre-menopausal women of childbearing potential one within 28 days prior to the start of study treatment and the other on Day 1 of the study prior to commencing treatment. Tests will be performed by the hospital's local laboratory. If results are positive the patient is ineligible/must be discontinued from the study. In the event of a suspected pregnancy during the study, the test should be repeated.

6.5 Patient-reported outcomes (PRO) (Not Applicable)

6.6 Pharmacokinetics (Not Applicable)

6.7 Pharmacogenetics (Not Applicable)

6.8 Health economics (Not Applicable)

7. BIOLOGICAL SAMPLING PROCEDURES

7.1 Volume of blood

The approximate total volume of blood that will be drawn from each patient in this study is as follows:

Table 5 Volume of blood to be drawn from each patient^a

Assessment	Sample volume (mL)	No. of samples	Total volume (mL)
Safety Clinical chemistry	6	8	48
Haematology	10	8	80
Tumour marker	4	8	32
Total	20	24	160

a Figures based on patient remaining on study for 6 months. However the number of samples is only an estimate and will vary depending on the length of time a patient stays on the study. Samples will be analysed at the local hospital laboratories and the volumes may vary slightly dependant on method

7.2 Handling, storage and destruction of biological samples (Not Applicable)

7.3 Labelling and shipment of biohazard samples (Not Applicable)

7.4 Chain of custody of biological samples (Not Applicable)

7.5 Withdrawal of informed consent for donated biological samples (Not Applicable)

8. ETHICAL AND REGULATORY REQUIREMENTS

8.1 Ethical conduct of the study

The study will be performed in accordance with ethical principles that have their origin in the Declaration of Helsinki and are consistent with ICH/Good Clinical Practice, applicable regulatory requirements and the AstraZeneca policy on Bioethics and Human Biological Samples.

8.2 Patient data protection

The Informed Consent Form will incorporate (or, in some cases, be accompanied by a separate document incorporating) wording that complies with relevant data protection and privacy legislation.

8.3 Ethics and regulatory review

An Ethics Committee should approve the final study protocol, including the final version of the Informed Consent Form(s) including any other written information and/or materials to be provided to the patients.

The investigator will ensure the distribution of these documents to the applicable ethics committee and to the study site staff.

The opinion of the Ethics Committee should be given in writing. The investigator should submit the written approval to AstraZeneca before enrolment of any patient into the study.

The Ethics Committee should approve all advertising used to recruit patients for the study.

AstraZeneca should approve any modifications to the Informed Consent Form that are needed to meet local requirements.

If required by local regulations, the protocol should be re-approved by the Ethics Committee annually.

Before enrolment of any patient into the study, the final study protocol, including the final version of the Informed Consent Form, is approved by the national regulatory authority or a notification to the national regulatory authority is done, according to local regulations.

AstraZeneca will handle the distribution of any of these documents to the national regulatory authorities.

AstraZeneca will provide Regulatory Authorities, Ethics Committees and Principal investigators with safety updates/reports according to local requirements.

AstraZeneca will be responsible for informing the regulatory authorities of SAEs/SUSARs as per the EU clinical trial directive and/or local country regulations and guidelines.

Each principal investigator is responsible for providing the Ethics Committees/IRB with reports of any serious and unexpected adverse drug reactions from any other study conducted with the investigational product. AstraZeneca will provide this information to the principal investigator so that he/she can meet these reporting requirements.

8.4 Informed consent

The principal investigator(s) at each centre will:

- Ensure each patient is given full and adequate oral and written information about the nature, purpose, possible risk and benefit of the study.
- Ensure each patient is notified that they are free to discontinue from the study at any time.
- Ensure that each patient is given the opportunity to ask questions and allowed time to consider the information provided.
- Ensure each patient provides signed and dated informed consent before conducting any procedure specifically for the study.
- Ensure the original, signed Informed Consent Form is stored in the investigator's Study File.
- Ensure a copy of the signed Informed Consent Form is given to the patient.
- Ensure that any incentives for patients who participate in the study as well as any provisions for patients harmed as a consequence of study participation are described in the informed consent form that is approved by an Ethics Committee.

8.5 Changes to the protocol and informed consent form

Study procedures will not be changed without the mutual agreement of the International co-ordinating investigator, the principal investigator and AstraZeneca.

If there are any substantial changes to the study protocol, then these changes will be documented in a study protocol amendment and where required in a new version of the study protocol (Revised Clinical Study Protocol).

The amendment should be approved by each Ethics Committee and if applicable, also the national regulatory authority, before implementation. Local requirements should be followed for revised protocols.

AstraZeneca will distribute any subsequent amendments and new versions of the protocol to each Principal investigator(s). For distribution to Ethics Committee see Section 8.3.

If a protocol amendment requires a change to a centre's Informed Consent Form, AstraZeneca and the centre's Ethics Committee should approve the revised Informed Consent Form before the revised form is used.

If local regulations require, any administrative change will be communicated to or approved by each Ethics Committee.

8.6 Audits and inspections

Authorised representatives of AstraZeneca, a regulatory authority, or an Ethics Committee may perform audits or inspections at the centre, including source data verification. The purpose of an audit or inspection is to systematically and independently examine all study-related activities and documents, to determine whether these activities were conducted, and data were recorded, analysed, and accurately reported according to the protocol, Good Clinical Practice (GCP), guidelines of the International Conference on Harmonisation (ICH), and any applicable regulatory requirements. The investigator will contact AstraZeneca immediately if contacted by a regulatory agency about an inspection at the centre.

9. STUDY MANAGEMENT BY ASTRAZENECA

9.1 Pre-study activities

Before the first patient is entered into the study, it is necessary for a representative of AstraZeneca to visit the investigational study site to:

- Determine the adequacy of the facilities
- Determine availability of appropriate patients for the study
- Discuss with the investigator(s) (and other personnel involved with the study) their responsibilities with regard to protocol adherence, and the responsibilities of AstraZeneca or its representatives. This will be documented in a CSA between AstraZeneca and the investigator

9.2 Training of study site personnel

Before the first patient is entered into the study, an AstraZeneca representative will review and discuss the requirements of the Clinical Study Protocol and related documents with the investigational staff and also train them in any study specific procedures and the WBDC system utilised.

The Principal investigator will ensure that appropriate training relevant to the study is given to all of these staff, and that any new information relevant to the performance of this study is forwarded to the staff involved.

The Principal investigator will maintain a record of all individuals involved in the study (medical, nursing and other staff).

9.3 Monitoring of the study

During the study, an AstraZeneca representative will have regular contacts with the study site, including visits to:

- Provide information and support to the investigator(s).

- Confirm that facilities remain acceptable.
- Confirm that the investigational team is adhering to the protocol, that data are being accurately and timely recorded in the eCRFs, that biological samples are handled in accordance with the Laboratory Manual and that investigational product accountability checks are being performed.
- Perform source data verification (a comparison of the data in the eCRFs with the patient's medical records at the hospital or practice, and other records relevant to the study) including verification of informed consent of participating patients. This will require direct access to all original records for each patient (eg, clinic charts).

The AstraZeneca representative will be available between visits if the investigator(s) or other staff at the centre needs information and advice about the study conduct.

9.3.1 Source data

Refer to the CSA for location of source data.

9.4 Study agreements

The Principal investigator at each centre should comply with all the terms, conditions, and obligations of the CSA for this study. In the event of any inconsistency between this Clinical Study Protocol and the CSA, the terms of Clinical Study Protocol shall prevail with respect to the conduct of the study and the treatment of patients and in all other respects, not relating to study conduct or treatment of patients, the terms of the CSA shall prevail.

Agreements between AstraZeneca and the Principal investigator should be in place before any study-related procedures can take place, or patients are enrolled.

9.4.1 Archiving of study documents

The investigator follows the principles outlined in the CSA.

9.5 Study timetable and end of study

The end of this study is defined as the date when all patients receiving olaparib have been followed for a minimum period of 6 months since start of treatment or the date of the final analysis of the data, whichever is the later. At this time point, the clinical study database will close to new data. Patients are however permitted to continue to receive study treatment beyond the closure of the database if, in the opinion of the investigator, they are continuing to receive benefit from treatment with olaparib. For patients who do continue to receive treatment beyond the defined end of study, investigators will continue to report all SAEs to AstraZeneca Patient Safety until 30 days after study treatment is discontinued, in accordance with Section 6.4.4 (Reporting of Serious Adverse Events). Additionally as stated in section 6.4.3 (Recording of adverse events), any SAE or non-serious adverse event that is ongoing at the time defined as the end of the study, must be followed up to resolution unless the event is considered by the investigator to be unlikely to resolve, or the patient is lost to follow-up.

The study may be terminated at individual centres if the study procedures are not being performed according to GCP, or if recruitment is slow. AstraZeneca may also terminate the entire study prematurely if concerns for safety arise within this study or in any other study with olaparib, or if results from any other study change the risk/benefit profile of olaparib.

10. DATA MANAGEMENT BY ASTRAZENECA OR DELEGATE

Data management will be performed by AstraZeneca Data Management Centre staff. The data collected through third party sources will be obtained and reconciled against study data.

Adverse events and medical/surgical history will be classified according to the terminology of the latest version the Medical Dictionary for Regulatory Activities (MedDRA). Medications will be classified according to the AstraZeneca Drug Dictionary. All coding will be performed by the Medical Coding Team at the AstraZeneca Data Management Centre.

Data queries will be raised for inconsistent, impossible or missing data. All entries to the study database will be available in an audit trail.

The data will be validated as defined in the Data Management Plan. Quality control procedures will be applied to each stage of data handling to ensure that all data are reliable and have been processed correctly.

When all data have been coded, validated and locked, clean file will be declared. Any treatment-revealing data may thereafter be added and the final database will be locked.

11. EVALUATION AND CALCULATION OF VARIABLES BY ASTRAZENECA

11.1 Calculation or derivation of efficacy variable(s)

Patients will undergo regular tumour assessments until documented objective disease progression as defined by RECIST 1.1 (see [Appendix C](#)).

At each visit, patients will be programmatically assigned a RECIST visit response of CR, PR, SD or PD depending on the status of their disease compared to baseline and previous assessments.

If a patient has had a tumour assessment, which cannot be evaluated, then the patient will be assigned a visit response of not evaluable (NE), unless there is evidence of progression, in which case the response will be assigned as PD.

For TL measurements, if $\leq 1/3$ of the TL sizes are missing then a scaling up rule will be applied as follows:

- If $\leq 1/3$ of lesions recorded at baseline are missing then the results will be scaled up (based on the baseline sizes) to give an estimated sum of diameters and this will be used in calculations (this is equivalent to comparing the visit sum of diameters of the non-missing lesions to the baseline sum of diameters excluding the lesions that are missing and determining at what rate the lesions are changing)
- If $> 1/3$ of lesions recorded at baseline are missing then the target lesion response will be NE. However, if the sum of non-missing target lesion diameters would result in PD (i.e. if using a value of 0 for missing lesions the sum of diameters has still increased by $> 20\%$ or more compared to the smallest sum of diameters on study and has an absolute increase ≥ 5 mm) PD takes precedence over NE
- A visit response of CR will not be allowed if any of the TL data is missing

11.1.1 Primary Endpoint

Tumour Response

Patients who have a confirmed CR or PR prior to progression or commencement of subsequent anti-cancer therapies will be classified as responders for the primary endpoint, tumour response. Tumour Response is defined as the percentage of patients who are responders.

A confirmed response of CR/PR means that a response of CR/PR is recorded at one visit and confirmed by repeat imaging at least 4 weeks later with no evidence of progression between confirmation visits.

Patients with measurable disease at baseline will be considered to have a visit response if they meet the visit response criteria for CR or PR. Patients with non-measurable disease at baseline will only be considered to have a visit response if they meet the visit response criteria for CR.

A visit response of CR is defined when all target and non-target lesions present at baseline have disappeared (with the exception of lymph nodes which must be < 10 mm to be considered non-pathological) and no new lesions have developed since baseline. A visit response of PR is defined when the sum of diameters of the TLs has decreased by 30% or more compared with baseline (with no evidence of progression) and the NTLs are at least stable with no evidence of new lesions.

11.1.2 Secondary Endpoints

Objective Response Rate (ORR)

A 'measurable disease' population will be derived for the analysis of ORR, DOR and DCR and will exclude patients who do not have measurable disease at entry.

ORR is defined as the percentage of patients who have a confirmed CR or PR prior to any evidence of progression (as defined by RECIST 1.1).

Progression free survival (PFS)

PFS is defined as the time from start of treatment until objective disease progression as defined by RECIST 1.1 or death (by any cause in the absence of progression).

Patients who have not progressed or died at the time of the statistical analysis will be censored at the time of their last evaluable RECIST assessment. Similarly, patients who start subsequent anti-cancer therapy prior to documented objective progression will be censored at the time of their last evaluable RECIST assessment. If a patient has no RECIST follow up assessments or has no evaluable baseline assessment and is still alive at the time of the analysis then they will be censored at 0 days for PFS. Symptomatic deterioration will not be regarded as a progression event.

Overall survival

Overall survival is defined as the time from start of treatment until death by any cause.

Patients who have not died at the time of the statistical analysis will be censored at the time they were last known to be alive.

Duration of response (DoR)

Duration of response is defined as the date of first documentation of response (CR/PR) until the date of disease progression as defined by RECIST 1.1 or death (by any cause in the absence of disease progression).

Disease Control Rate (DCR)

Disease Control Rate is defined as the percentage of patients who have at least one visit response of CR or PR or who have demonstrated SD for a minimum interval of 16 weeks following start of treatment.

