Haematology /clinical chemistry/urinalysis	X	
Pregnancy test ^a		X
Blood sample for disease-specific marker ^b		X
Tumour Assessment (CT or MRI according to RECIST 1.1) ^c	X	
Adverse Events (from time of consent)	X	X
Concomitant medications	X	X
Confirmation of pre-existing documented BRCA mutation status	X	

^a Pre-menopausal women of child-bearing potential must have a negative urine or serum pregnancy test within 7 days prior to starting treatment and a confirmatory test before treatment at visit 1. In the event of suspected pregnancy during the study, the test should be repeated and, if positive, the patient discontinued from study treatment immediately

^b Known tumour markers should be measured eg, CA-125 for ovarian cancer, CA15-3 for breast cancer, CEA for colorectal cancer.

^c RECIST 1.1 assessments will be performed using CT or MRI scans of the appropriate anatomical area applicable to the tumour under investigation. Baseline assessments should encompass all areas of known predilection for metastases in the disease under evaluation and should additionally investigate areas that may be involved based on signs and symptoms of individual patients. Baseline assessments should be performed no more than 28 days before the start of study treatment, and ideally should be performed as close as possible to the start of study treatment.

Table 2 Study schedule – on treatment and follow up

(See section 6.2 for Further details)

Visit number	2 ^a	3	4	5 ^a	6 ^a	7 ^a	^a Visit 8, 10, 12 etc onwards (Note that all visits after visit 7 are monthly but assessments vary depending on visit number)	Visit 9, 11, 13 etc onwards	Treatment Discontinuation	Follow-up 30 days after last dose of study medication	Survival Every 8 weeks following treatment discontinuation
Day	1	8	15	29	57	85	(ie, days 113, 169, 225 etc)	(ie, days 141, 197, 253 etc)			
Visit Window		±1d	±1d	±3d	±3d	±3d	±3d	±3d	±3d	±3d	±7d
Physical exam	X ^b			X	X	X	X	X	X		
Vital signs, body weight (Includes BP [supine position], pulse and temperature)	X ^b			X	X	X	X	X	X	X	
ECOG performance status	X ^b			X	X	X	X	X	X	X	
ECG & urinalysis ^c					X					X	
Haematology & clinical chemistry	X ^b	X	X	X	X	X	X	X	X	X	
Pregnancy test before treatment	X										
Blood sample for disease-specific marker	X			X	X	X	X	X	X		
Tumour Assessment (CT or MRI according to RECIST) ^d					X		X		X		
Adverse Events	X	X	X	X	X	X	X	X	X	X	
Concomitant medications	X	X	X	X	X	X	X	X	X	X	

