6.2.3.4 CT or MRI scans (RECIST 1.1)

Baseline and follow-up contrast-enhanced CT of the specific sites appropriate to the patient's tumour should be performed with other regions where clinically indicated for the adequate assessment of tumour burden. All baseline radiological tumour assessments must be performed no earlier than 28 days before the start of study treatment. Scans that were

performed as part of standard of care prior to signature of the informed consent form can be analysed for the purposes of the study if they were performed within the correct time frame and of sufficient quality. Subsequent tumour assessments according to RECIST should be performed at the end of every 8 weeks (+/-1 week) up to 6 months after starting treatment and then every 12 weeks thereafter according to the planned study schedule (see [Table 2](#)) up to objective progression by RECIST 1.1 ([Therasse et al 2000](#)). Any other sites at which new disease is suspected should also be appropriately imaged. Patients must be followed until RECIST disease progression.

Tumour evaluations using CT/MRI according to RECIST will continue in the study until the data cut-off for the analysis. At this point investigators will be notified that CT/MRI for study purposes are no longer required.

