12.2.2.5 Disease Control Rate (DCR)

The DCR will be summarised in patients included in the 'measurable disease' population.

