12.3 Determination of sample size

No formal sample size calculation has been performed since the study is considered exploratory in nature. Up to 150 patients will be recruited to the study. It is intended that there will be at least 20 patients in each of the breast, ovarian, prostate and pancreatic tumour type groups in order to provide descriptive information on the effect of olaparib treatment on tumour response in a variety of tumour types.

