4. TUMOUR RESPONSE EVALUATION

4.1 Schedule of evaluation

Baseline assessments should encompass all areas of known predilection for metastases in the disease under evaluation and should additionally investigate areas that may be involved based on signs and symptoms of individual patients and should be performed no more than 28 days before the start of study treatment. Follow-up assessments will be performed every 8 weeks +/- 1 week after the start of treatment up to 6 months and then every 12 weeks thereafter until objective disease progression as defined by RECIST 1.1. Any other sites at which new disease is suspected should also be adequately imaged at follow-up.

If an unscheduled assessment was performed and the patient has not progressed, every attempt should be made to perform the subsequent assessments at their scheduled visits. This schedule is to be followed in order to minimise any unintentional bias caused by some patients being assessed at a different frequency than other patients.

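### The 16-week minimum for stable disease in DCR falls exactly on the nominal second scan, so non-responders scanned early within the window and with no later SD scan are counted as not controlled

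*Protocol*

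**What the plan says.** Section 11.1.2 gives two routes to disease control. One is "at least one visit response of CR or PR". The other is for patients "who have demonstrated SD for a minimum interval of 16 weeks following start of treatment". No allowance for the scan window is attached to the second route.

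Section 6.2.3.4 has scans "performed at the end of every 8 weeks (+/-1 week) up to 6 months after starting treatment". Section 6.3.2 gives the same window, and Appendix C Section 4.1 repeats it: "every 8 weeks +/- 1 week after the start of treatment up to 6 months and then every 12 weeks thereafter". In Table 2 (Section 3.1) the first on-treatment scan is at Day 57. Later scans fall in the visit column headed "days 113, 169, 225 etc", and that table gives these visits a window of ±3 days.

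Section 12.2.2.5 covers the analysis: "The DCR will be summarised in patients included in the 'measurable disease' population". Section 12.3 describes the study as a whole: "No formal sample size calculation has been performed since the study is considered exploratory in nature".

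**The concern.** A minimum duration that must be shown on a scan needs to be reachable on every scan that the protocol accepts as the scan for that time point. Here the threshold lies at the centre of the permitted window. Nearly half of the permitted days come before it, and a patient with SD on one of those days has shown slightly less than 16 weeks of SD.

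If the next scan again shows SD, nothing is lost. If it shows PD, or if the patient dies or has no further evaluable scan, the patient is counted as not controlled because of the date of a compliant scan. DCR would then depend partly on how sites book scans within the window.

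**Working it through.** **Calendar check (protocol figures only).** Scans are 8 weeks (56 days) apart and Day 1 is the first dose.

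- Second scan: 1 + 2 × 56 = Day 113, which reproduces Table 2.
- Time since start: (113 − 1)/7 = 16.0 weeks, exactly the cut-off.
- Window ±1 week: 105 to 119 days after start, or 15 permitted days. Seven of them (105 to 111) are below 112 days: 7/15 = 47%.
- Window ±3 days: 109 to 115 days, or 7 permitted days. Three are below 112: 3/7 = 43%.

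**Who is affected.** Compare two patients with no CR or PR, SD at the second scan and PD at the week-24 scan. The one scanned on Day 112 (111 days after start) is not controlled. The one scanned on Day 113 (112 days) is.

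**Size (rests on assumptions).** The protocol gives no PFS figure and no distribution of scan days. I assume exponential PFS with survivor function S(t), medians of 3.7, 5.5 and 7 months (112.6, 167.4 and 213.1 days at 30.44 days per month), and scan days uniform and independent within the window. Among non-responders:

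loss = (share of scans early) × [mean S over the early days − mean S over the week-24 window]

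For the 5.5-month median and ±1 week: 7/15 × (0.6395 − 0.4989) = 0.0656, or 6.6 points. SD at the week-16 scan is 62.9%, so the strict rule gives 62.9 − 6.6 = 56.3%.

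| Median PFS (months) | SD at week-16 scan | Strict 112-day rule | Loss, ±1 week | Loss, ±3 days |
|---|---|---|---|---|
| 3.7 | 50.2% | 42.8% | 7.4 | 6.5 |
| 5.5 | 62.9% | 56.3% | 6.6 | 5.8 |
| 7 | 69.5% | 63.7% | 5.8 | 5.2 |

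A simulation of 400,000 patients under the same assumptions agrees to within 0.1 point (strict rule 42.8, 56.4 and 63.6%).

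**Allowing for responders.** Anyone with a visit CR or PR is controlled whatever the scan date. If a fraction r respond and the rest follow the same curve, the loss in overall DCR is (1 − r) × the figures above.

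- r = 20%, ±1 week: 0.8 × 5.8 to 0.8 × 7.4 = 4.7 to 5.9 points.
- r = 40%, ±1 week: 0.6 × 5.8 to 0.6 × 7.4 = 3.5 to 4.4 points.
- ±3 days: 4.1 to 5.2 points at r = 20%, and 3.1 to 3.9 at r = 40%.

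**Scan timing at the extremes.** If every scan is on time or late, the loss is zero. If every week-16 scan is early by one to seven days, the loss among non-responders is 12 to 16 points over these medians (for example 0.6395 − 0.4989 = 14.1 points at 5.5 months).

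**With a 105-day cut-off.** Every in-window week-16 scan qualifies, so DCR among non-responders equals the proportion with SD at that scan and the loss is zero.

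**The case against.** The strongest objection is that window allowances and the date that ends an SD interval are programming rules, normally left to an SAP, and the SAP is not at hand. That holds for details on which the protocol is silent, but the protocol is not silent on the number. It states a minimum of 16 weeks, and an SAP accepting 15 weeks would depart from it. The mismatch is therefore in the protocol.

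A second objection is that a strict minimum may be a deliberate, conservative choice. It may be. The protocol does not say that SD at the week-16 scan is the target, so the loss above is measured against a natural reference rather than a stated one. A deliberate minimum would still treat two compliant patients with the same scan results differently.

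Three stronger readings are tempting and are not supported:

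- **That scan timing rather than disease decides who is controlled.** It decides only for non-responders with SD on an early week-16 scan and no later SD scan. At a 5.5-month median that is 6.6 of the 62.9 points with SD at that scan.
- **That the full 6 to 7 points applies to this trial.** That figure assumes no responders. Section 1.2 reports confirmed response rates at 400 mg bd of 11/27 (40.7%) and 11/33 (33.3%) in breast and ovarian cancer, and Section 3.2 expects these tumour types to form the majority. The larger figure is more relevant to tumour types with few responders.
- **That DCR could be overstated by 8 to 12 points.** This requires timing SD to the date of PD, so that PD on an on-time or late week-16 scan counts as controlled. The wording requires SD to have been demonstrated for the interval, and Section 11.1 assigns that visit PD. The reading is strained, and naming the qualifying assessment would close it off.

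**Conclusion.** The point holds in a limited form. Followed literally, the 16-week minimum drops compliant patients whose week-16 SD scan was early and who have no later SD scan.

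The calendar arithmetic is certain. The size is not: about 6 to 7 points with no responders, about 3.5 to 6 points with 20 to 40% responders, about 3 to 5 points for the same responder range with ±3 days, and zero if all scans are on time or late. These figures rest on exponential PFS with medians of 3.7 to 7 months, uniform scan days, and non-responders following the same curve. None of these comes from the protocol.

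Importance is modest. DCR is a descriptive secondary endpoint with no test, threshold or decision attached, and the primary tumour response rate is unaffected.

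**What to change.** In Section 11.1.2, define DCR as the percentage of patients with "at least one visit response of CR or PR", or with SD recorded at an evaluable assessment 15 weeks (105 days) or more after start of treatment. The 105 days is 16 weeks minus the one-week scan window. Tying the rule to a recorded SD assessment also settles that the interval is measured to an SD scan and not to the date of PD.

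Reconcile the ±3 days in Table 2 with the ±1 week in Sections 6.2.3.4 and 6.3.2 and Appendix C Section 4.1. The 105-day cut-off covers the earliest permitted scan under either window (105 or 109 days), so it need not wait for that.

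The cost is one sentence, with no change to data collection. The downside is that some patients will count with 15 rather than 16 weeks of SD, which the report should state.
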